3.1.1 Part 1: Helmet Deployment in Controls

3.1.1.1 Screening Phase

For Part 1 of this pilot study, the study team will recruit 4 normal controls (or dummies) using flyers placed around the University of Pennsylvania. The study team will obtain informed consent, and review inclusion/exclusion criteria to confirm eligibility.

3.1.1.2 Study Intervention Phase

After the study team obtains informed consent and eligibility is confirmed, normal control participants (defined as non-pregnant participants without epilepsy or other diagnosis that may result in falls) will be given helmets and asked to fall straight over onto their right or left side onto a padded surface. Falls will be witnessed and video recorded by the study team. If the participant significantly attempts to break their

fall and the helmet does not deploy, they may be asked to fall again. If the helmet inflates in 3 out of 4 falls, we will proceed with Part 2. If the helmet does not inflate in at least 3/4 falls, we will stop the study.

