3.1 General Design

We propose to investigate the safety of the Hövding helmet device in patients with DRE. While the Hövding helmet is commercially marketed in Europe, it has not been specifically used in a defined epilepsy population. Our project would aim to analyze the safety of the use of the device during 5 seizures from a standing position. For Part 1 of this pilot study, the study team will test helmets on 4 normal controls (or dummies) and have subjects fall directly over onto their sides on a padded floor and record whether or not the helmet deploys. Assuming that the helmet deploys in at least 3/4 of the 4 falls in this scenario as we believe it will, we would proceed to the next phase of the trial.

For Part 2, we propose to enroll 20 subjects from our DRE population who suffer frequent seizures Some patients are already identified and their seizure frequency is documented in a database maintained at the University of Pennsylvania. We will also accept referrals from outside providers and review their records of seizure type, frequency, age, and pregnancy status to see if their patients qualify for the study.

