5.1 Description

The Hövding inflatable helmet is designed for cyclists as a collar with a deployable airbag that inflates when a sensor detects rapid changes in acceleration. When the cyclist encounters a crash, the airbag deploys and wraps the back and sides of the user's head in inflated nylon fabric which then slowly deflates after deploying. Its design is meant to be unobtrusive and fashion conscious to encourage greater compliance among the cyclist population; it is tested to a higher pounds per square inch standard than the current industry requirements for conventional bicycle helmets in the EU. Part 1 of this study, where normal controls (or dummies) are asked to fall from standing onto a padded surface while wearing the helmet, will address whether a fall outside of the context of cycling is sufficient for airbag deployment. If so, we will begin part 2 of the study.

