8.3.3 Safety Analysis

All subjects entered into the study and randomized at the baseline visit will have detailed information collected on adverse device effects (ADE) for the overall study safety analysis.

8.3.3.1 Part 2

• N/A

8.3.3.2 Part 2

• Compare the rates of injury and post concussive syndromes in subjects where the helmet inflated during a seizure related fall to seizure related falls where the helmet did not inflate.

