9.5 Stopping Rules

In Part 1, if 3/4 of the helmets do not inflate due to a fall from standing in normal controls or dummies, the study will not move on to Part 2.

10 Study Administration, Data Handling and Record Keeping

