12.1 Risks

12.1.1 Part 1

Risk may include possible injury from the fall, however, serious injury is not expected as they will be falling on a padded surface. Another possible risk is injury from the helmet deployment. It is possible that participants may have other adverse device effects that we cannot predict.

12.1.2 Part 2

This study will confirm the design and operating specifications before beginning an extensive clinical trial. Performance of this device in this limited study serves to establish the parameters for a larger clinical study. This will be the first trial of this helmet in subjects with drug resistant epilepsy and frequent seizures. It is possible that subjects may have other adverse device effects that we cannot predict.

Risks and adverse device effects that could reasonably be expected to occur include:

- The helmet deploys in a situation not related to a seizure: This risk is possible as the helmet has previously been designed to work in cycling. Activities that have rapid accelerations and decelerations such as running, jumping, or playing sports could potentially increase the chances of the helmet deploying.
- The helmet does not deploy during a seizure: As stated above, the helmet has not been previously optimized for use in this setting and, as such, may not deploy during a seizure.
- Abrasions to the back of the neck when the helmet deploys
- Suffocation: Considered to be very rare as when the helmet deploys, it leaves the face and mouth open and the helmet gradually deflates. No reports of suffocation or near suffocation have been reported despite its commercial availability in Europe over the past 3 years.
- Injury to those around the subject when the helmet deploys, if when deploying the subject is near other people
- Temporary hearing impairment after helmet deployment
- Discomfort from wearing the helmet collar

The risk of falling is not actually an increase in risk from the usual state of participants and there is no increased risk of fall or injury resulting from fall with study participation.

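### The rule for opening Part 2 counts helmet inflations only, and the planned safety analysis is worded for randomised subjects, so Part 1 device effects are collected but tied to neither

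*Combined protocol and SAP*

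**What the plan says.** The go/stop rule appears in four places, each time in terms of inflation.

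- Section 3.1.1.2: "If the helmet inflates in 3 out of 4 falls, we will proceed with Part 2", and its converse, "If the helmet does not inflate in at least 3/4 falls, we will stop the study".
- Section 3.1: "Assuming that the helmet deploys in at least 3/4 of the 4 falls in this scenario", the trial moves on.
- Section 5.1: Part 1 "will address whether a fall outside of the context of cycling is sufficient for airbag deployment", followed by "If so, we will begin part 2 of the study".
- Section 9.5, the only entry under Stopping Rules: Part 2 does not open "if 3/4 of the helmets do not inflate due to a fall from standing in normal controls or dummies".

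The sole Part 1 endpoint is the deployment rate (sections 3.2.1.1 and 8.1). Harm is nevertheless foreseen. Besides injury from the fall, section 12.1 says of Part 1: "Another possible risk is injury from the helmet deployment". Table 1 schedules an assessment of ADEs, unanticipated ADEs and unanticipated problems at the Part 1 visit.

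On analysis, section 8.3.3 says: "All subjects entered into the study and randomized at the baseline visit will have detailed information collected on adverse device effects (ADE"), for the overall safety analysis. Two sub-entries follow, both headed Part 2. The first reads N/A. The second compares injury and post-concussive syndrome between seizure-related falls with and without inflation.

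**The concern.** The title presents the trial as a safety pilot, and section 1.1.2 reports no clinical research data on the helmet. The Part 1 falls are the ones the study team witnesses and records on video, so they are the best-observed deployments in the study. Yet the ADE assessment made there feeds no stated decision and no stated analysis.

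Two things are at stake. If a volunteer were hurt by a deployment, the rule as written would still say proceed, and any hold would rest on judgement outside it. And the final safety summary, if produced as section 8.3.3 words it, would leave out people who wore the helmet and had it inflate on them. If dummies replace all the volunteers, as several sections allow, the rule can be met with no human deployment seen in this study at all.

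**Working it through.** The plan gives no operating characteristics for its rule (section 8.2 is N/A), so there is no figure to reproduce. The check has four steps.

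**1. Does injury enter the rule?** Let p be the probability that the helmet inflates in a staged fall, and q the probability that an inflation injures. Neither is in the documents, so both are assumptions, treated as independent. The rule in section 3.1.1.2 gives

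P(go) = 4p³(1−p) + p⁴.

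- p = 0.5: 0.313
- p = 0.8: 0.4096 + 0.4096 = 0.819
- p = 0.9: 0.2916 + 0.6561 = 0.948
- p = 0.95: 0.986

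The formula contains no q. The result is the same if every inflation injures.

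To show what this insensitivity means, suppose purely for illustration that the rule also required no injury:

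P(go) = 4p³(1−p)(1−q)³ + p⁴(1−q)⁴.

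| q | p = 0.8 | p = 0.9 |
|---|---|---|
| 0.10 | 0.567 | 0.643 |
| 0.25 | 0.302 | 0.331 |
| 0.50 | 0.0768 | 0.0775 |
| 1.00 | 0 | 0 |

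This is not a proposed criterion.

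**2. How much could Part 1 show about injury?** The chance of at least one injury in 4 deployments is 1 − (1−q)⁴: 0.186 at q = 0.05, 0.344 at q = 0.10 and 0.590 at q = 0.20. If none is seen, the one-sided 95% upper bound on q is 1 − 0.05^(1/4) = 52.7% for 0 of 4, and 1 − 0.05^(1/3) = 63.2% for 0 of 3. A clean Part 1 is weak reassurance. An observed injury would be informative.

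**3. Who is in the safety analysis?** Randomisation is described only for Part 2 (sections 3.1 and 3.1.2.1). Section 8.3.3 refers to randomised subjects. Its one specified comparison concerns seizure-related falls, which cannot occur in Part 1. The only population in section 8.4 is the all-randomised one, for helmet versus no-helmet comparisons. The description of adverse events is a Part 2 secondary endpoint (sections 3.2.2.2 and 8.1.1.2). No planned analysis therefore takes in Part 1 ADEs.

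**4. Do the four statements of the rule agree?** Not when exactly 2 of 4 inflate. Section 3.1.1.2 stops the study. Section 9.5, read literally, stops it only when 3 of 4 fail, so 2 inflations would pass. The probability of landing there is 6p²(1−p)²: 0.375 at p = 0.5 and 0.154 at p = 0.8. At p = 0.5 the chance of proceeding is 0.313 under one section and 0.688 under the other.

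**The case against.** The best answer is that Part 1 harm sits inside a full safety pathway. Under section 9.2 all events are recorded from consent and reviewed by the principal investigator and the sponsor's medical director. Section 9.3 has them classified for relatedness, expectedness and seriousness. Section 9.4 sends them to the IRB and FDA, asks for new information on increased risk within 10 days, and provides for withdrawal of approval. None of this is limited to Part 2. Section 12.2.1 also hopes that Part 1 will help justify continuing, which is broader than inflation. The Study Summary refers to a separate Data and Safety Monitoring Plan, which is not among the documents.

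Much of this stands, and it rules out several stronger readings that a reader might infer:

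- That an injury could not hold Part 2. It could, through the investigator, IRB or FDA; it is simply not part of the written rule.
- That Part 1 events disappear. They are in the safety record, and missing only from the planned analysis.
- That these would be the first deployments on people. The helmet is already sold in Europe, so at most they are the first in this study.
- That Part 1 supplies some calculable share of all deployments. The 5 evaluable seizures in section 4.5.2 are a minimum, non-seizure deployments are also expected, and dummies would make the human share of Part 1 zero.
- That the N/A entry in section 8.3.3 certainly refers to Part 1. It is headed Part 2, so this is only probable.

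The pathway does not close the gap on timing. Under section 9.4.1, related but anticipated events go to the IRB at continuing review and to the FDA annually. A non-serious deployment injury is arguably anticipated, since section 12.1.1 names it. In a study planned for 1 year, that report could come after Part 2 has begun.

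**Conclusion.** The point holds in a limited form. The step to Part 2 has no pre-specified safety component, no section requires the Part 1 ADE review to be complete before Part 2 opens, and section 8.3.3 as worded leaves Part 1 volunteers out of the planned safety analysis. The first two statements are subject to what the unseen monitoring plan may contain.

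The rule's indifference to injury is exact and needs no assumption; the probabilities quoted rest on assumed p and q. The statistical weight is small, since at most four planned falls cannot establish safety. The value lies in acting on an injury, and reporting it, if one is seen. The change is worth making because the data are already scheduled for collection.

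**What to change.** 1. In sections 3.1, 3.1.1.2, 5.1 and 9.5, make opening Part 2 require a documented review of the Part 1 ADE assessments as well as the inflation count. The criterion is for the sponsor-investigator and IRB to set. If the Data and Safety Monitoring Plan already requires such a review, cite it there instead.
2. State that Part 1 yields no human safety information if only dummies are used.
3. Reconcile sections 3.1.1.2 and 9.5 for the case of exactly 2 inflations in 4.
4. In section 8.3.3, define the device-safety set as every subject exposed to the helmet in either part. List Part 1 ADEs per deployment, separately from Part 2 because the setting and population differ.
5. Correct the duplicate Part 2 headings in section 8.3.3 and say which part the N/A entry covers.

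The cost is protocol wording, a short review of up to four assessments already scheduled, and possibly a brief pause between the parts.

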3.1.2 Part 2: Helmet Deployment During Seizures

3.1.2.1 Visit 1: Screening Phase

20 subjects with high seizure frequencies (greater than one seizure every 2 months and at least 1 seizure every 6 months that could result in a fall) will be recruited. The primary method of recruiting subjects for this study will be reviewing the epilepsy database at the University of Pennsylvania and communicating with attending neurologists about whether it is appropriate to introduce the study to potential subjects. We will offer participation in the trial as part of their standard of care visits in the neurology office. We expect that 20 subjects will be sufficient in this preliminary study to determine safety and to suggest efficacy. Written consent from subject or legally authorized representative (LAR) will be obtained prior to any study procedures being conducted.

At visit 1, the following procedures will be performed:

- Subjects or LARs will sign Informed Consent prior to any study activities
- Medical History
- Demographics
- Physical Exam including height, weight, and neck circumference
- Urine Pregnancy Test (if female of childbearing potential)
- Randomization
- Dispense Helmet, if applicable
- Dispense Seizure Calendar
- Dispense Seizure Questionnaire
- Dispense Helmet Deployment Questionnaire (if subject is assigned to wear a helmet)
- Dispense Rivermead Post Concussive Scale (for patients able to complete scale)

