1.1.2 Clinical Data to Date

To date, there is no available clinical research data on the Hövding Inflatable Helmet.

2 Study Objectives

The overall objective is to conduct a pilot study of the use of the Hövding helmet in patients with risk of head injury as a result of seizures to help plan a larger study to determine the safety and efficacy of the helmet for this indication. Ultimately, we hope to demonstrate that its use decreases the rate or severity of head injuries due to seizures that occur from standing. This study will help confirm the assumed safety of this device for use in patients with seizures, estimate the effect size, and pilot the use of novel patient-administered outcome instruments and a previously validated post concussive syndrome scale.

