This is a single-center, randomized, 2-way crossover study design. Using block randomization, enrolled participants will be assigned to first enter either the "helmet" or "no helmet" group following consent and confirmation that they meet all inclusion and none of the exclusion criteria. At the time of a seizure that results in a fall, subjects will be asked to fill out a questionnaire to help document the circumstances of the seizure and if any injuries occurred. If the patient seeks medical attention, their medical records will be reviewed afterwards. If a head injury is sustained, they will be asked to fill out the Rivermead Post Concussive scale 48 hours after their seizure in order to quantify their head injuries.² If the subject was wearing a helmet at the time of the fall and it deploys, or of the helmet deploys for any other reason, subject or their representatives will be asked to fill out an additional questionnaire detailing the circumstances of its deployment. After the helmet deploys, we will ask subjects to return their helmets to the University of Pennsylvania for Sponsor assessment. After this fall, or after any helmet deployment, subjects in both groups will be asked to return to the University of Pennsylvania for a study visit during which they will switch groups. If a subject is enrolled for 3 months without experiencing a seizure resulting in fall, they will be considered a screen fail.

During their participation in both groups, subjects will be asked to fill out a daily seizure calendar to help document the frequency of seizures and seizure types.

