4.5 Total Number of Subjects

4.5.1 Part 1

Recruitment will end when 4 subjects are enrolled.

4.5.2 Part 2

Recruitment will end when approximately 20 subjects are enrolled, in order to document at least 5 evaluable seizures during helmet wear.

4.6 Vulnerable Populations:

N/A

5 Study Intervention

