8.2 Sample Size and Power Determination

N/A

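### Twenty subjects, tied to at least 5 helmet seizures, cannot determine the helmet's safety as sections 3.1.2.1 and 4.3.2 say they will

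*Combined protocol and SAP*

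**What the plan says.** The same sentence appears in sections 3.1.2.1 and 4.3.2: "We expect that 20 subjects will be sufficient in this preliminary study to determine safety and to suggest efficacy".

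The rest of the plan bears on it as follows.

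- Section 4.5.2 gives the reason for the number: "Recruitment will end when approximately 20 subjects are enrolled, in order to document at least 5 evaluable seizures during helmet wear".
- Section 3.1 states the safety aim on the same count, without the words that make it a minimum: "Our project would aim to analyze the safety of the use of the device during 5 seizures from a standing position".
- The section titled "8.2 Sample Size and Power Determination" reads N/A. Section 8.3 lists comparisons and descriptive statistics but names no test, interval or precision target.
- The only stopping rule (section 9.5) concerns deployment in Part 1. Part 2 has no safety criterion.
- Section 2 describes the pilot's role as "to help plan a larger study to determine the safety and efficacy of the helmet for this indication". It adds: "This study will help confirm the assumed safety of this device for use in patients with seizures". Section 1.1.2 says there are no clinical data on the device so far.

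**The concern.** The repeated sentence is the plan's only statement of what the Part 2 sample size delivers, and on safety it is a strong one. It has no calculation or decision rule behind it. It also conflicts with section 2, where determining safety is the task of a later, larger study.

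What is at stake is how a clean result is read. Section 12.1.2 says performance here is to set the parameters for a larger study. If few helmet falls occur and none causes harm, the protocol's own wording would allow that to be described as safety determined, when a high harm rate per fall would still be compatible with the data.

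**Working it through.** **The plan's own figure.** Neither 20 nor 5 can be reproduced, because no alpha, power, effect size, event rate or precision target is given. What can be checked is what the stated numbers deliver.

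**How many helmet falls are possible.** The design section says: "This is a single-center, randomized, 2-way crossover study design". Subjects leave their current group after the first seizure with a fall or after any helmet deployment (sections 3.1, 3.1.2.4 and 5.2). Each subject therefore gives at most one index helmet fall, about 20 in all. A deployment outside a seizure ends the helmet period without one. A subject with no fall in 3 months is a screen fail.

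For an indicative yield, assume Poisson falls at rate λ per month, 10 subjects per sequence and full wear:

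- P(first fall within 3 months) = 1 − e^(−3λ).
- P(first fall within 3 months and second within 6) = 1 − e^(−3λ) − 3λe^(−6λ).
- One fall per 6 months (λ = 1/6): 0.393 and 0.393 − 0.184 = 0.210. Expected helmet falls = 10 × 0.393 + 10 × 0.210 ≈ 6. By simulation, the chance of at least 5 is 77%. About 12 of 20 subjects become screen fails.
- Three falls per 6 months (λ = 1/2): 0.777 and 0.777 − 0.075 = 0.702. Expected helmet falls ≈ 15.

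The entry criterion is one seizure per 6 months that *might* cause a fall, so the true fall rate could lie on either side of the first case.

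**Safety: no events in n helmet falls.** The exact (Clopper-Pearson) upper 95% bound is 1 − 0.05^(1/n) one-sided and 1 − 0.025^(1/n) two-sided.

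| Event-free helmet falls | One-sided | Two-sided |
|---|---|---|
| 5 (stated minimum) | 45% | 52% |
| 10 | 26% | 31% |
| 15 | 18% | 22% |
| 20 (approximate ceiling) | 14% | 17% |

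Put another way, with 5 falls a harm occurring in 20% of helmet falls is missed entirely with probability 0.8^5 = 33%, and a 10% harm with probability 0.9^5 = 59%. Excluding a 10% harm rate would take 29 event-free falls one-sided or 36 two-sided. Both exceed the ceiling.

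**Efficacy, for illustration only.** The one helmet effect in the document is an odds ratio of 0.31 for motorcycle helmets (section 1.1). The head-injury risk per unprotected fall is not given, so 30% and 50% are assumed.

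- 30% without a helmet: odds 0.429 × 0.31 = 0.133, a risk of 11.7% with one.
- 50% without a helmet: odds 1 × 0.31 = 0.31, a risk of 23.7% with one.

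Exact power of a two-sided 5% Fisher test, treating falls as independent and ignoring the crossover pairing:

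| Helmet v no-helmet falls | 30% risk | 50% risk |
|---|---|---|
| 5 v 5 | 1.8% | 6.2% |
| 20 v 20 | 19% | 30% |

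The plan promises no test, so direction is a fairer yardstick. The chance that the helmet rate comes out lower at 5 v 5 is 63–72% under this odds ratio, against 36–38% with no effect. At 20 v 20 it is 90–95% against 43–44%.

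**The case against.** The strongest defence is that this is a pilot and mostly says so. The sentence calls the study preliminary and promises only to suggest efficacy. Section 2 aims to estimate the effect size, and section 12.2.2 calls the device experimental. Five is a minimum, and with frequent falls the yield could approach 15 to 20. No rule says that zero events would be reported as safety established, and moving from a pilot to a larger trial does not require excluding any particular harm rate.

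Much of this stands. A reader might infer that the study can deliver nothing on efficacy either. The documents do not support that. To suggest is not to test at 5%, and no test or alpha is planned. Neither the odds ratio nor the per-fall risks used above are design inputs, and even at 5 v 5 an extreme split such as 0 of 5 against 4 of 5 gives p = 0.048. At the minimum a signal is very unlikely under these assumptions, not impossible, and towards 20 v 20 the direction of the difference becomes moderately informative. Nor do the documents show that the sponsor would misreport a clean result. They only leave wording that permits it.

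The defence does not rescue the safety claim. That claim is to determine, not to suggest. Section 3.1 itself frames the safety aim on 5 seizures, and even the ceiling leaves a bound of 14% to 17%. Counting wearers instead of falls does not help: the bound for 20 wearers is the same, and a subject who starts without the helmet and screen-fails never wears it.

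**Conclusion.** As regards safety, the sentence is wrong as written. With no events, the upper 95% bound on harm per helmet fall runs from 45% one-sided (52% two-sided) at the stated minimum to 14% (17%) at the approximate ceiling, so no attainable yield determines safety. This rests only on the binomial model and on one index helmet fall per subject. The sentence also contradicts section 2 and has nothing behind it in section 8.2.

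On efficacy the conclusion is narrower: very weak evidence at 5 helmet falls, with illustrative power of 2–6% at 5 v 5 and 19–30% at 20 v 20. Those figures depend on an assumed odds ratio of 0.31 and an assumed no-helmet injury risk of 30–50% per fall. The indicative yields of about 6 and 15 helmet falls depend on assumed fall rates and full wear.

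A reader might also take this as a finding that the pilot is too small and should enrol more. It is not. A feasibility pilot of this size can be reasonable; the fault lies in what the plan says the size achieves.

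**What to change.** 1. **Sections 3.1.2.1 and 4.3.2.** Replace the sentence with: *The size is chosen for feasibility, to collect preliminary safety data and to estimate injury rates for planning a larger study.*
2. **Section 8.2.** Replace N/A with: *With no events in 5, 10, 15 or 20 helmet falls, the exact upper 95% confidence bound on risk per fall is 45%, 26%, 18% or 14% one-sided (52%, 31%, 22% or 17% two-sided). Injury and device-effect rates will be reported with exact confidence intervals. Absence of events will not be interpreted as establishing safety.*
3. **Section 2.** Reword the sentence "This study will help confirm the assumed safety of this device for use in patients with seizures" so that the study will collect preliminary data on the safety of the device in these patients.

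The text should not go further and rule out any conclusion on safety or efficacy. That would bar a conclusion of harm if serious device injuries occurred, and it would conflict with the primary objective in section 2.2.1 of comparing injury rates.

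The cost is wording and the calculation of exact intervals. No patients, visits or procedures are added. The stated claim becomes less favourable.
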